  - c. *Technical:* Access to all electronic files will be limited to CITI-trained research team members. Audio recordings of the focus groups will be destroyed after transcription. Electronic data will be stored on secure servers housed at DHMC with appropriate backup and will be shared across the research team using the research team's password-protected SharePoint site hosted by Dartmouth.

2. **Online message testing (Phase 2)** - Once the list of strong candidate themes is finalized, we will test the effects of those theme-relevant messages/materials on changing knowledge, attitudes, beliefs, and behavioral intentions of parents of children 9-14 years old living in New Hampshire and Vermont; (parents of any age child are invited to complete the survey as well, excluding questions related to vaccination history and intention to vaccinate). The message testing phase will involve pre/post-test designs. Prior to the message-testing phase (Phase 2), if needed, we will conduct anonymous online pilot surveys through Qualtrics. Prior to the message testing, this pilot test is to check the validity of each message (e.g., ensuring that the stimulus materials -campaign messages- are presented and perceived by audiences as we intended for positive effects).

To test the persuasion effects of candidate messages, we will measure an array of constructs in the pre-test stage (before exposure to materials/messages). A list of the candidate constructs that are critical in understanding message effectiveness include: prior knowledge, pre-existing attitudes, normative beliefs, response efficacy, and issue involvement. After finishing pre-test assessments, participants will be randomly assigned to one of the conditions and asked to read/review the stimulus material/message while experimentally controlling for high elaboration likelihood. After the message exposure step, participants will be asked to answer post-test survey measures, including: persuasiveness of the viewed message/material, attitude toward behavior promoted, response efficacy, behavioral intention, and normative belief assessment. A full list of finalized survey questionnaires and messages will be submitted in a future modification to this study, before the online message testing commences.

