- a) *Sample size and recruitment:* We expect to test a finalized set of messages, up to approximately 40 messages, with up to 30 people evaluating each message; as such, we will recruit maximum 1,200 people to complete message testing via various media recruitment and platforms (including Amazon Mechanical Turk and social media advertisements). For message testing

[figure not shown]
experiments, we implement two different cohort studies (Cohort 2A and 2B in Figure 1). Additional people will be screened for eligibility.

**Cohort Phase 1B:** Previously IRB-approved Cohort 1B is no longer part of this study design. We did not have large enough sample size to conduct a time-lag follow-up study, thus this Cohort 1B is removed from the project.

**Cohort Phase 2A:** We use paid advertisements on social media and MTurk to recruit residents in VT and NH. An external link to Qualtrics surveys will be embedded in the ads and in the MTurk posting. The message testing study will be held on Qualtrics. We will measure same constructs and examine an identical set of candidate messages across two cohorts. This cohort will not have a time-lag between pre- and post-assessments.

**Cohort Phase 2B:** We will implement the same message testing study and recruit participants in the US via Mturk and social media advertisements (e.g., Facebook ads). MTurk is an online labor market with more than 500,000 active members where requesters distribute small tasks, and workers complete the tasks for compensation as low as 1 cent in US dollars. More than 345,000 tasks are available on MTurk to anonymous workers to complete. The cohort will be invited to the same message-testing experiments with identical pre- and post-assessments used in Cohort 1B and Cohort 2A. The data from this national pool of participants will be used as reference points. This cohort does not have a time-lag between pre- and post-assessments.

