**b) Data collection methods:** After recruitment, we will screen participants for eligibility (criteria described below) with a Qualtrics-administered survey that asks the participant a series of questions that include the eligibility criteria as well as some dummy questions, to avoid deception on part of the prospective participant (see enclosed pre/post test survey). They will be asked to read the information sheet to proceed. Once they click the NEXT button to provide implicit consent to participate in the study, they will be asked to click on a link to the survey hosted on Qualtrics. They will be asked to answer pre-test questions. Cohort 1B will end survey and will be followed-up later for a random assignment for message exposure and post-assessments (for those who provide email address or MTurk worker ID number). After finishing pre-test, (without any time-lag), participants in Cohort 2A and 2B will be randomly assigned to one of the advertisement/message conditions in the following page. For message exposure, participants will be asked to carefully view the assigned message/material, and then answer a series of post-test questions. When participants finish the entire questionnaires, they will be debriefed and provided with useful resources about HPV. MTurk participants (Cohort 2B) will be asked to enter their worker ID (to verify their participation for compensation on Amazon Mechanical Turk). Eligible participants recruited from social media (Cohort 2A and 2B) who want to receive study compensation will have a chance to enter their contact email address for one of e-gift cards (to be sent to randomly selected participants). Eligible participants recruited from MTurk (Cohort 2A, and 2B) will be asked to provide their MTurk Worker ID number before being paid (amount described below). See enclosed document with examples of messages that participants could be exposed to/randomized to.

**c) Participant compensation:** Participants recruited from social media platforms (Cohort 2A and 2B) will have a chance to receive one of 50 e-gift cards worth up to \$10. Participants recruited through MTurk will be compensated as MTurk workers using their worker ID numbers. We estimate the screening questionnaire to take approximately up to 5 minutes and will compensate

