people up to \$0.50 for completing the screener. We estimate the actual survey/message testing to take about 15 minutes per participant. For those recruited through MTurk, based on typical MTurk payment amounts and based on [name] extensive experience with MTurk, we estimate each MTurk worker to receive up to \$1.50 for 15 minutes of message testing. This payment amount is in-line with typical payment amounts expected on MTurk (\$0.10/minute).

- d) *Eligibility:* Participants must be parents with at least one child who is 9-14 year old child living in New Hampshire or Vermont to complete the entire survey as part of Cohort 2A and in the US for Cohort 2B (parents with any age children are invited to complete the survey, excluding questions related to vaccination history and intention to vaccinate their 9-14 year old child/ren). The survey will contain a set of screening questions (as described earlier) to determine eligibility; geographic eligibility will be determined based on self-reported zip code/state and geo-targeting tools available on social media platforms.
- e) *Confidentiality and Protections:* Data will be collected online through Qualtrics. Any electronic data will be stored on password-protected computers and will only be viewable to CITI-trained research team members through Qualtrics portal and/or through this project's Dartmouth-hosted SharePoint site that is only accessible to the research team members via password. After data are no longer needed, they will be destroyed by the research team, and destruction will be confirmed by the information technology team at the Norris Cotton Cancer Center/Geisel School of Medicine. Further, participants will not be asked to reveal their names or social security numbers. We will ask demographic information, but these self-reported responses will be anonymized and paired with a random Study ID number. Responses will never be linked to any identifying information.

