#### 4. Analysis

**Describe any qualitative tests and measures as well as quantitative methods:**

1. **Online and local focus groups and message testing (Phases 1 & 2)-** Facebook comments, survey comments, and transcripts/audio files of the focus groups will be reviewed by the research team and coded for themes. We will also perform content and linguistic analyses. The self-reported survey measures will be examined for outliers and data skewness. Recording, transformation, or standardization will be made when necessary. We will conduct chi-square statistics for categorical variables and employ repeated GLM, ANOVA, ANCOVA, or regression statistics for continuous multivariate variables while controlling for relevant covariates. We will take structural equation modeling or path analyses to model persuasion pathways from message/ad exposure to changes in behavioral intentions to vaccinate. Based on persuasiveness scored rated for the HPV vaccine messages/ads, we will statistically test and select the

most highly-ranked messages/ads (best candidate messages/ads). These selected messages/ads will be used for the social media campaign.

2. **Social media campaign (Phase 3)-** We will measure message effectiveness by analyzing each message's effectiveness by assessing engagement data (provided by social media campaign metrics), and key constructs, including attitudes and intent to vaccinate (to be assessed via online survey embedded in the social media campaign messages). See enclosed survey; parents with children of any age are invited to complete all questions except for questions related to vaccination history and intention to vaccinate their 9-14 year old child/ren, which are limited to parents with 9-14 year old children. We will compare the differences between the two audience segments (rural vs. urban) or other subgroups of interest that emerge from the data. Although we do not solicit comments on Facebook, we expect that some Facebook users may leave comments/questions anyway; we will analyze the comments for themes and linguistic characteristics and compare between rural and urban audiences or by campaign themes (research team will de-identify all comments prior to analyses).

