### **10. Recruitment**

**Describe method(s) of recruitment. Associated advertisements and other materials to be used for recruitment should be uploaded to the 'Consent Forms and Recruitment Materials' page in Rapport.**

1. **Online focus groups/survey and message testing (Phases 1 & 2) -** Participants will be recruited from Amazon Mechanical Turk and social media platforms such as Facebook and Twitter to discuss the topics and to evaluate messages/ads. See enclosed recruitment messaging.
2. **Social media campaign (Phase 3)-** Ads, messaging content, and/or posts will be presented to social media (e.g., Facebook) users. Those users who click on the content for more information will be invited to participate in the evaluation survey (same process as used during Phase 2). We are not soliciting Facebook comments but some Facebook users may leave comments anyway..

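### As described, Phase 2 can rank messages but cannot show that any message improves attitudes or increases intent, because no unexposed condition is named and pre- and post-test share one session

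*Combined protocol and SAP*

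**What the plan says.** Section 3, Online message testing (Phase 2), sets the aim: "we will test the effects of those theme-relevant messages/materials on changing knowledge, attitudes, beliefs, and behavioral intentions of parents". Participants answer a pre-test, and then, with no time lag, "participants in Cohort 2A and 2B will be randomly assigned to one of the advertisement/message conditions in the following page". They view the assigned message and complete the post-test.

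Item a) of the same part says neither cohort has an interval between the two assessments, and that the former time-lag cohort has been dropped. It calls the national Cohort 2B a source of reference points, but the cohorts do not differ in exposure: "We will measure same constructs and examine an identical set of candidate messages across two cohorts". The ceiling is 1,200 people, described in Section 9.a as 40 messages with 30 parents each.

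Section 4 lists repeated GLM, ANOVA, ANCOVA, regression and path models with covariates, and selects campaign messages by ranked persuasiveness. It names no contrast with an unexposed group.

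The Phase 3 part of Section 3 says that the messages identified so far improve attitudes and increase intent. Sections 6.a and 7 repeat this as a finding in a national sample. Part of Objective 1 (Section 2) is to measure effectiveness in changing attitudes and intentions.

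**The concern.** Two kinds of conclusion are drawn from Phase 2. One is relative: which messages are more persuasive. The other is absolute: that the messages improve attitudes and increase intent.

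Randomisation among messages supports the first. The second needs to know what would have happened between pre-test and post-test without a message. People asked the same questions twice within about 15 minutes may shift simply because they were asked, or because the pre-test made them think about HPV. If everyone sees a message, that shift and the message effect are a single quantity.

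At stake is the absolute claim. It answers the effectiveness part of Objective 1, introduces Phase 3, and is one of several supports for the risk and unexpected-event statements. A reader would take it as a demonstrated message effect.

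**Working it through.** **1. The plan's own figure.** 40 messages x 30 people = 1,200, which reproduces the stated maximum. No alpha, power, effect size or SD is given, so there is no power calculation to reproduce.

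**2. What the design identifies.** Let t_m be the effect of message m and s a same-session shift common to all conditions.

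- Expected change in arm m: t_m + s.
- Message m versus message k: (t_m + s) - (t_k + s) = t_m - t_k, so s cancels.
- One arm's own change, or the pooled change: s stays in.
- An unexposed arm would have expected change s, which would make t_m estimable.

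Without such an arm, no method listed in Section 4 can recover s, because every analysed participant has seen a message. Cohort 2B does not help, since it sees the identical set. Phase 3 does not fill the gap either: "Those users who click on the content for more information will be invited to participate in the evaluation survey", so its respondents are also exposed.

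**3. How large the problem could be.** The documents give neither s, nor the pre-post correlation r, nor the test behind the claim. Assumed: s favourable, 0.02 to 0.2 SD; r = 0.5, 0.7 or 0.9; equal SD at both times; paired t-test at two-sided 5%. For an inert message (t_m = 0), the chance of a significant favourable change is the upper tail, beyond the two-sided critical value, of a noncentral t with n - 1 degrees of freedom and noncentrality s / sqrt(2(1 - r)/n).

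Example: n = 30, s = 0.1, r = 0.5. The standard error is sqrt(1/30) = 0.183, the noncentrality 0.55, and the probability 0.076.

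| n | shift (SD) | r = 0.5 | r = 0.7 | r = 0.9 |
|---|---|---|---|---|
| 30 (one message) | 0.1 | 0.076 | 0.101 | 0.219 |
| 30 | 0.2 | 0.184 | 0.277 | 0.658 |
| 600 pooled | 0.02 | 0.071 | 0.092 | 0.193 |
| 600 pooled | 0.05 | 0.231 | 0.351 | 0.781 |
| 1,200 pooled | 0.02 | 0.102 | 0.143 | 0.340 |
| 1,200 pooled | 0.05 | 0.409 | 0.608 | 0.972 |

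The nominal value is 0.025. The size of the national cohort is not given; 600 (half of 1,200) is an assumption and 1,200 is the upper limit.

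For intention n is smaller, because "parents with any age children are invited to complete the survey, excluding questions related to vaccination history and intention to vaccinate". If half of participants have a child aged 9-14 (an assumed share), 30 x 0.5 = 15 per message, and the same formula gives 0.055/0.068/0.125 at 0.1 SD and 0.108/0.152/0.365 at 0.2 SD.

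**4. Simulation check.** With 40 inert messages and one control, 30 people each, s = 0.2, r = 0.7 and 2,000 runs, own-arm tests were favourable about 28% of the time. Tests of change against control were significant about 5% of the time, and the F test among messages also stayed at 5%. The relative comparison is sound; the absolute one is not.

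**5. Precision with a control branch.** 36 x 30 + 120 = 1,200. The 95% half-width after adjustment for pre-test score is 1.96 x sqrt((1 - r^2)(1/n1 + 1/120)).

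- One message, n1 = 30: 0.35/0.29/0.17 SD at r = 0.5/0.7/0.9.
- All 36 pooled, n1 = 1,080: 0.16/0.13/0.08 SD.

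These are for attitudes. For intention, if half of participants answer, they widen to 0.49/0.40/0.25 and 0.23/0.19/0.12 SD.

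**The case against.** The strongest reply is that the point rests on an absence in incomplete text. Figure 1, the questionnaires and the message enclosures are not in the reviewed text, and a control may be described there. This stands, and it makes the point conditional. A reader might infer from 40 x 30 = 1,200 that there is no room for a control, but the counts are ceilings or approximate, so that does not follow.

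Second, message choice uses ranked persuasiveness between randomised conditions. This also stands: a reader who concludes that the campaign messages were wrongly selected goes beyond the documents. Likewise, Objective 1 starts with identifying messages, a relative task that the design supports. The risk statements also rest on comparison with everyday public service announcements and on response guidelines.

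Third, the shift is not shown to exist. It could be zero, which leaves the claim intact, or unfavourable, which would make the observed change understate the message effect. The documents do not support saying that the reported improvement is an artefact.

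Finally, a reader might infer that intention had no baseline. The pre-test constructs named are "prior knowledge, pre-existing attitudes, normative beliefs, response efficacy, and issue involvement", while the post-test includes "attitude toward behavior promoted, response efficacy, behavioral intention, and normative belief assessment". But the first list is of candidate constructs, and Section 4 plans "to model persuasion pathways from message/ad exposure to changes in behavioral intentions to vaccinate", so a baseline may well exist. The lists do not settle it.

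**Conclusion.** The point holds for the absolute claims only. On the text as written, the statements in Sections 3 (Phase 3), 6.a and 7 that the messages improve attitudes and increase intent, and the effectiveness part of Objective 1, cannot be separated from a repeat-questioning shift of unknown size and sign. Between-message comparisons and message selection are unaffected.

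The probabilities above illustrate favourable shifts under assumed values and do not estimate what happened. Per message they are moderate at 0.1 SD. In a pooled test even 0.02-0.05 SD matters, to a degree that depends on the unstated size of the national cohort. The upper ends depend on r = 0.9. The conclusion also rests on there being no control condition in the material not seen.

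**What to change.** Unless Figure 1 or the enclosures show a control condition, reword the three statements and the effectiveness part of Objective 1 to say that these messages were rated most persuasive among those tested, and report pre-to-post change as uncontrolled. If Phase 2 is complete, as the Phase 3 text suggests, the cost is one query to the sponsor and the wording.

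If any Phase 2 testing remains, reserve a no-message or unrelated-message branch within the 1,200, for example 36 x 30 + 120. Estimate the average message effect as post-test score versus control, adjusted for pre-test score, and state how many parents of 9-14 year-olds answered the intention item. The cost is one more survey branch, no extra participants, and about four fewer messages.

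Single-message contrasts would stay imprecise (half-width 0.17-0.35 SD for attitudes), so the pooled contrast (0.08-0.16 SD) should be the main one. A contrast for the selected messages in the data that selected them would look too favourable and should be labelled so.

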## 2. Objectives and Hypotheses

Related to the online focus groups, message testing, and social media components:

[figure not shown]
- 1) Identify HPV vaccine themes/messages/materials and measure their effectiveness to change parent attitudes and intentions to vaccinate their adolescent children;
- 2) Describe any differences in message/material effectiveness for parents residing in rural areas versus parents residing in urban areas
- 3) Launch a social media campaign with the most effective messages to improve parent attitudes.

[figure not shown]

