- d) *Eligibility:* For Facebook recruitment, we will geo-target the Facebook ads to recruit from predominantly-rural ZIP codes and predominantly-urban ZIP codes (as defined by Rural-Urban Commuting Area (RUCA) Codes). Anyone viewing the ad will be eligible to leave comments. Those people interested in answering the private survey (whether recruited through Facebook) will need to confirm their ZIP code, state of residence, and that they have a child 9-14 years old for inclusion, as eligibility will be limited to parents with children 9-14 years old living in New Hampshire or Vermont. In addition to our actual screening questions to ensure the prospective participant meets our eligibility criteria, we will ask some dummy questions, to avoid deception.

As needed, we may post additional advertisements to Facebook just to recruit for survey completion (without inviting people to leave public comments).

e) *Confidentiality and Protections:* For the online focus group comments, Facebook users viewing the ad will receive a disclaimer that any comments will be publicly-available and viewable by others (See enclosed recruitment messaging). For the private surveys, data will be collected online through Qualtrics and on paper for people participating in the local focus groups (described below). Any electronic survey data will be stored on password-protected computers and will only be viewable to CITI-trained research team members through Qualtrics portal and/or through this project's Dartmouth-hosted SharePoint site that is only accessible to the research team members via password. After data are no longer needed, they will be destroyed by the research team, and destruction will be confirmed by the information technology team at the Norris Cotton Cancer Center/Geisel School of Medicine. Further, participants who provide their contact information will do so via a separate survey link to ensure their contact information is collected and maintained separate from their survey data. We will ask demographic information, but these self-reported responses will be anonymized and paired with a random Study ID number. Responses will never be linked to any identifying information.

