3. **Social media campaign (Phase 3):** The purpose of Phase 3 is to implement and evaluate an educational social media campaign for the public. Based on the results of Phase 1 and 2 studies to-date, we have identified a set of strong messages that improve parent attitudes and increase parents' intent to vaccinate their 9-14 year old child/ren for HPV. We will use these tested messages to launch a social media-based campaign via the Norris Cotton Cancer Center's Facebook page. We will deploy up to six campaign messages (see enclosed document with messages) to two groups of parents using Facebook's geo-targeting features, based on users' zip codes: 1) Parents in rural NH and VT and 2) Parents in urban NH and VT. We will measure each message's effectiveness by analyzing engagement data (provided by social media campaign metrics—all aggregate data with no individual identifiers), and attitudes and intent to vaccinate (to be assessed via online survey embedded in the social media campaign messages). See enclosed survey; parents with children of any age are invited to complete all questions except for questions related to their intention to vaccinate, which are limited to parents with 9-14 year old children. We will compare the differences between the two audience segments (rural vs. urban) and other subgroups that emerge from the data..

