3. **Online message testing (Phase 2)** - The information sheet will be displayed on the first page of the online survey implemented on Qualtrics (for participants recruited from MTurk and social media) before the web-based survey starts. Participants who want to participate in the study will be asked to carefully read the overview of the study described in the information sheet (provide their anonymous MTurk worker ID for MTurk workers), and click “NEXT” to complete the implicit consent process. See enclosed information sheet.
4. **Social media campaign (Phase 3)**- Social media users who click on the ad will be presented with an opportunity to participate in the evaluation survey. The information sheet will be displayed on the first page of the online survey implemented on Qualtrics before the web-based survey starts. Participants who want to participate in the study will be asked to carefully read the overview of the study described in the information sheet and click “NEXT” to complete the implicit consent process. See enclosed information sheet (which is slightly modified from the previously approved information sheet used in Phase 2). Because the ads offer a platform where users can leave comments and interact with others, some users may leave comments; we will provide a similar disclaimer to what we used during Phase 1 (previously approved by IRB; only edit is addition of Virginia Commonwealth University to the text). The disclaimer will be part of the ad, the first comment under the ad, or the 2nd image in the carousel ad setting for high visibility. The disclaimer text will read:

a) “Please Note: Regarding comments on this post, researchers at Dartmouth College and Virginia Commonwealth University will use your comments below for RESEARCH purposes to learn about people’s views on the HPV vaccine. Leaving comments and participating is completely voluntary, and we will NOT collect your name or any other identifying information. Please note: your comments on this post may be publicly available.

b. Waiver(s) or alteration(s) may be requested for research that involves no more than minimal risk.

Indicate requested waiver(s) or alteration(s) below. In addition, complete the corresponding section of the [Waivers and Alterations Request Form](#) and upload it to the 'Consent Forms and Recruitment Materials' page in Rapport.

- For the informed consent *process*
- For the *documentation* of informed consent

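### Phase 3's post-click survey has no pre-exposure or unexposed comparison, so it describes people who clicked and cannot estimate an effect of the campaign or of a message

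*Combined protocol and SAP*

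**What the plan says.** Section 3, item 3, opens: "The purpose of Phase 3 is to implement and evaluate an educational social media campaign for the public". Objective 3 in Section 2 reads: "Launch a social media campaign with the most effective messages to improve parent attitudes". The Phase 3 entry in Section 9b gives education as the main goal, but also says that the campaign's effectiveness is being evaluated.

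Two measures of effectiveness are named in Section 3 and again in Section 4:

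- Engagement: "We will measure each message's effectiveness by analyzing engagement data". These are aggregate platform metrics.
- Survey: "attitudes and intent to vaccinate (to be assessed via online survey embedded in the social media campaign messages".

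Access to the survey is described twice. Section 11a: "Social media users who click on the ad will be presented with an opportunity to participate in the evaluation survey". Section 10: "Those users who click on the content for more information will be invited to participate in the evaluation survey".

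The stated Phase 3 comparisons are rural against urban, subgroups that emerge from the data and, for comments only, campaign themes. Section 5 lets the team raise or lower the budget of each ad according to reach and engagement.

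**The concern.** To say that a message or campaign was effective on attitudes and intent is to say that it changed them. That needs a measurement the campaign has not touched: the same people earlier, a comparable unexposed group, or randomised alternatives. No Phase 3 text describes any of these. The survey sees only people who were shown an ad, chose to click it and then agreed to answer.

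At stake is what Phase 3 can conclude. A favourable average could mean that the campaign moved parents, or that favourable parents clicked. A gap between two messages, or between rural and urban respondents, has the same two readings. Delivery of the educational campaign is not affected.

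**Working it through.** Phase 3 has no calculated sample size or test to reproduce. The check is one of design, with a short illustration.

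**1. Order of events.**

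- Phase 2 (Section 3, item 2): pre-test questions, random assignment to a message, viewing, post-test questions.
- Phase 3 (Sections 10 and 11a): ad shown, click, information sheet and consent, survey.

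In Phase 3 every survey answer follows exposure.

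**2. What the survey mean contains.** For message m, the mean answer among completers is A(m) + C(m). A(m) is their mean attitude before exposure and C(m) is the mean change. Only the sum is observed. Between messages 1 and 2 the observed difference is [A(1) − A(2)] + [C(1) − C(2)]. Selection common to both messages cancels; selection that differs does not. Phase 2 measures A before the assigned message and randomises the message. Phase 3 does neither, and budget shifts can further change who is reached by each ad.

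**3. Why numbers do not help.** Inputs from the plan: six messages and two audiences (Section 3), and no more than 2,000 completers expected (Section 9b). At that ceiling, 2,000 / (6 × 2) = 167 per cell. My assumptions: equal split, SD 1, two-sided 5% test, no effect of any message, and a pre-exposure difference of 0.1 to 0.3 SD between the two groups compared. The SE of a difference is sqrt(2/n):

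- 167 against 167: sqrt(2/167) = 0.109 SD, so 0.2 SD is 0.2/0.109 = 1.8 SE.
- 1,000 against 1,000 (rural against urban at the ceiling): sqrt(2/1000) = 0.045 SD, so 0.2 SD is about 4.5 SE.

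| Pre-exposure difference | Significant, 167 per group | Significant, 1,000 per group |
|---|---|---|
| 0.1 SD | 15% | 61% |
| 0.2 SD | 45% | 99% |
| 0.3 SD | 78% | >99% |

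A larger survey makes selection more likely to be read as an effect. Intent cells will be smaller still, since only parents of 9-14 year-olds answer those items.

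**4. Would any unexposed group do?** Suppose 1,000 campaign-ad clickers are compared with 300 people who clicked a neutral ad. SE = sqrt(1/1000 + 1/300) = 0.066 SD. If the two ads attract people who differ by 0.2 SD, the bias is 0.2/0.066 = 3.0 SE. The ad that recruits must therefore be the same on both sides of the comparison.

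**The case against.** **The survey may contain a pre-test.** Section 10 says that clickers "will be invited to participate in the evaluation survey (same process as used during Phase 2", and Phase 2 used pre- and post-test questions. The survey itself is an enclosure that is not in the documents, so one cannot say that it has no such items. It would not matter: in Phase 3 the way in is the campaign ad, so even the first item follows exposure. At most such items would bracket a second viewing inside the survey.

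**Phase 2 has already shown that the messages work.** Sections 3, 6 and 7 rely on this, and it is real evidence on message content. It comes from assigned viewing within a survey, where participants were told to look carefully. It does not show what an ad in a Facebook feed did, and Phase 3 sets out to measure attitudes and intent again.

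**The main goal is education, and objective 3 is to launch.** This stands as a limit on importance. But Sections 3, 4 and 9b still promise an assessment of effectiveness.

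**Stronger readings the documents do not support.**

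- A reader might infer that Phase 3 can evaluate nothing. Engagement data are the first-named measure and can describe reach and response; they do not show attitude change.
- A reader might infer that messages drawing already favourable parents will come out best. That is possible, but the documents specify no Phase 3 survey statistic and give neither direction nor size for the selection.
- A reader might infer that comparing messages on engagement alone is a clean substitute. It is not: display depends on Facebook's algorithm (Section 9a), and spend follows engagement (Section 5).
- A reader might infer that a control is already provided for. The Phase 1 text says only that "we may post additional advertisements to Facebook just to recruit for survey completion". It concerns Phase 1 and does not say that those ads carried no message. It is a precedent, not a control arm.

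**Conclusion.** The point holds for the survey component. Attitudes and intent in Phase 3 are measured only after exposure, only among people who clicked, without a baseline, an unexposed group or random assignment to messages. The survey can describe those respondents. It cannot attribute their answers to the campaign or rank messages by the change they produced.

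The size of any bias cannot be derived from the documents; the percentages above rest on an assumed 0.1 to 0.3 SD difference and are illustrative. The conclusion that the effect is not identified does not depend on them. It limits what may be concluded, not whether the campaign can run, and is worth correcting before launch because a baseline cannot be recovered later.

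**What to change.** **Minimum.** In Section 3 (Phase 3), Section 4 (item 2) and Section 9b (item 4), state that the post-click survey describes the attitudes and intent of people who clicked. State also that neither it nor the non-randomised engagement comparisons estimate an effect of the campaign or of a message. Say whether the Phase 3 survey has pre and post items and, if so, what they bracket. This costs only wording.

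**Preferred, in addition.** Field the same survey through one identical neutral survey-only ad, carrying no campaign message, to the same rural and urban audiences shortly before launch and again after the campaign. Compare the two waves, adjusting for rurality and child age group. Adjust for vaccination history only among parents of 9-14 year-olds, who alone answer that item and the intent items. Using the same ad in both waves avoids comparing campaign-ad clickers with neutral-ad clickers. Section 9a expects reach above 75% of the intended audience, so the first wave must be completed before launch.

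For planning, with SD 1, 80% power and a two-sided 5% test (all assumed), n per wave = 2 × (1.96 + 0.84)² / d². This gives about 393 for 0.2 SD and 175 for 0.3 SD, before any allowance for ZIP-code clustering.

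**Cost and limits.** A small ad spend and one extra ad text for review. Respondents remain volunteers in both waves, and a before-and-after comparison does not remove time trends; both should be stated with the results. Recruitment is a risk: Section 3 records that a follow-up cohort was dropped because the sample was too small. If a wave falls short, the minimum wording still applies.
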